6.2 Statistical Analysis Methods

The statistical analyses will be reported using summary tables, listings, and figures (TLFs). The International Council for Harmonisation (ICH) numbering convention will be used for all TLFs.

Continuous variables will be summarized using descriptive statistics (number of subjects, mean, median, standard deviation, minimum, and maximum).

Categorical variables will be summarized by counts and by percentages of subjects in corresponding categories.

Baseline is defined as the last non-missing assessment prior to the first dose of OP-1250. If an assessment is on the same date as first dose of OP-1250 and time of assessment is not recorded, the assessment will be considered to have occurred prior to the first dose.

All summary tables will be presented with separate columns for each OP-1250 dose. Individual subject data obtained from the eCRFs, external vendors, and any derived data may be presented by subject in data listings.

The analyses described in this plan are considered a priori, in that they have been defined prior to database lock.

All analyses, tabulations, and graphical presentations will be performed using SAS® software version 9.4 or higher.

7. NOTATION OF VISITS

Table 1: Visit Terminology

Visit	Notation Used
Screening	Screening/Baseline ^a
Baseline, Cycle 1 Day 1	Baseline
Cycle 1 Day 8	C1D8
Cycle 1 Day 15	C1D15
Cycle 2 Day 1	C2D1
Cycle 2 Day 15	C2D15
Cycle 3 Day 1	C3D1
Cycle 3 Day 15	C3D15
Cycle 4 Day 1	C4D1
Cycle 4 Day 15	C4D15
Cycle X Day 1 ^b	CXD1
Treatment Termination	Treatment Termination

^a Assessments from screening visit may be used for baseline if they are last assessment before first dose of study drug.

^b Visits will continue on Day 1 of each cycle until subject terminates treatment.

8. ANALYSIS SETS

8.1 Enrolled Analysis Set

The enrolled analysis set (ENR) includes all subjects who enrolled into the study after signing an informed consent form and satisfying inclusion/exclusion criteria.

8.2 Safety Analysis Set

The safety analysis set (SAF) will include all subjects who received at least 1 full or partial dose of OP-1250. Subjects will be analyzed according to the OP-1250 doses they actually received as a first dose. The safety analysis set will be used for all safety analyses except for the analyses of DLTs.

8.3 DLT Evaluable Analysis Set

The DLT evaluable analysis set (DLTAS) includes all subjects in the dose escalation portion of the study who either received at least 75% of the OP-1250 planned doses or experienced a DLT during Cycle 1. Subjects who do not receive the minimum dosing requirement for a reason other than DLT will be regarded as non-evaluable and may be replaced.

8.4 Full Analysis Set

The full analysis set (FAS) includes all subjects who received at least 1 dose of OP-1250 and have at least 1 post-baseline tumor assessment.

8.5 Efficacy Analysis Set

The efficacy analysis set (EFS) will include all subjects who received at least 1 cycle of OP-1250 and have at least 1 post-baseline tumor assessment.

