#### **8.4 Subject Identification and Replacement of Subjects**

Each subject will be assigned a unique subject identifier. This unique identifier will be on all case report form (CRF) pages. Subjects in Part A (Dose Escalation) of the Phase I portion who are not DLT evaluable (as defined in [Section 8.8.2](#)) may be replaced as appropriate. DLT evaluable is defined as a subject who experienced a DLT and/or received at least 75% of the originally assigned doses in the first cycle. Subjects who withdraw from study before receiving 75% of the planned doses in the first cycle of treatment for reasons other than a DLT unrelated to study drug toxicity will be considered to have inadequate data to support dose escalation decisions.

Subjects in Part B (Dose Expansion) of the Phase I portion and subjects in the Phase II portion will be replaced if they are not evaluable for response (ie, received less than 1 cycle of therapy and/or did not have a post-baseline tumor assessment).

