#### Overall Response Rate:

Subjects with measurable disease who receive at least 1 cycle of OP-1250 and have a post treatment tumor assessment will be included in the determination of the ORR. [REDACTED]

[REDACTED] The estimate of the ORR will be accompanied by 2-sided 95% exact confidence intervals. The ORR will be determined using RECIST 1.1 (see [Appendix E](#)) for the entire body (which include both CNS and non-CNS disease) [REDACTED]

Subjects without measurable disease will not be included in the determination of ORR; however, they will be included in safety, secondary, and exploratory analyses where appropriate.

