10. EFFICACY ANALYSES

Efficacy analyses for ORR [REDACTED] by investigator assessment will be conducted using EFS with measurable disease at baseline (without cohort C). CBR by investigator assessment will be summarized using CBR analysis set. [REDACTED]

[REDACTED]

[REDACTED]

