10.1 Efficacy Endpoints

ORR

ORR is the primary efficacy endpoint in phase II (without cohort C) and secondary endpoint in phase I. Objective response will be determined using RECIST version 1.1. The overall tumor response at each time point will be recorded. A subject's best overall response will be derived as the best response over all time points, where responses from best to worst are CR, PR, SD, progressive disease (PD), and not evaluable (NE). Time point responses after the first assessment of PD will not be used in the derivation of confirmed best objective response. A confirmed response requires a CR or PR to be confirmed at a subsequent tumor assessment at least 4 weeks (28 days) from the initial assessment of CR or PR, and a confirmed response of SD requires the interval from first dose date to SD to be at least 6 weeks (42 days). To determine the best overall confirmed response in the presence of at least one time point response of CR or PR, the best response for each pair of assessments will be derived based on Table 2. The best overall confirmed response will then be the best over all of the pair best responses.

Table 2: Derivation of Best Overall Response when confirmation of CR and PR required

Overall response for 1 st time point	Overall response for subsequent time point	Best overall response for pair of assessments
CR	CR	CR if time requirement is met, otherwise NE
CR	PR	SD or PD or PR ^a
CR	SD	SD provided minimum criteria for SD duration met, otherwise, PD
CR	PD	SD provided minimum criteria for SD duration met, otherwise, PD
CR	NE	SD provided minimum criteria for SD duration met, otherwise NE
PR	CR	PR

PR	PR	PR
PR	SD	SD
PR	PD	SD provided minimum criteria for SD duration met, otherwise, PD
PR	NE	SD provided minimum criteria for SD duration met, otherwise, NE
NE	NE	NE

CR=complete response; PR=partial response; SD=stable disease; PD=progressive disease; NE=not evaluable.

^a : If a CR is truly met at first time point, then any disease seen at a subsequent time point, even disease meeting PR criteria relative to baseline, makes the disease PD at that point (since disease must have reappeared after CR). Best response would depend on whether minimum duration for SD was met. However, sometimes 'CR' may be claimed when subsequent scans suggest small lesions were likely still present and in fact the patient had PR, not CR at the first time point. Under these circumstances, the original CR should be changed to PR and the best response is PR.

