The confirmed ORR is defined as the proportion of subjects with a best overall response of confirmed CR or PR in EFS with measurable disease at baseline.

The secondary efficacy endpoints for Phase II are:

CBR

CBR is defined as the proportion of subjects with a confirmed CR, PR, or SD and who had been on treatment for ≥ 24 weeks. Subjects who had disease progression per RECIST 1.1 7 days before Cycle 7 day 1 will not be considered as clinical benefit. Duration of treatment is defined as time from the first dose date of study treatment to end of treatment date for subjects discontinued treatment or to data cutoff date for ongoing subjects.

CBR will be summarized based on CBR Analysis Set (without cohort C) defined in 8.6.

[REDACTED]

[REDACTED]

[REDACTED]

[REDACTED]	[REDACTED]	[REDACTED]
------------	------------	------------

[REDACTED]	[REDACTED]	[REDACTED]
[REDACTED]	[REDACTED]	[REDACTED]
[REDACTED]	[REDACTED]	[REDACTED]
[REDACTED]	[REDACTED]	[REDACTED]

[REDACTED]

[REDACTED]

[REDACTED]

[REDACTED]

[REDACTED]	[REDACTED]	[REDACTED]
[REDACTED]	[REDACTED]	[REDACTED]
[REDACTED]	[REDACTED]	[REDACTED]
[REDACTED]	[REDACTED]	[REDACTED]

[REDACTED]	[REDACTED]	[REDACTED]
[REDACTED]	[REDACTED]	[REDACTED]
[REDACTED]	[REDACTED]	[REDACTED]

[REDACTED]

[REDACTED]

[REDACTED]

[REDACTED]

[REDACTED]	[REDACTED]	[REDACTED]
[REDACTED]	[REDACTED]	[REDACTED]
[REDACTED]	[REDACTED]	[REDACTED]
[REDACTED]	[REDACTED]	[REDACTED]
[REDACTED]	[REDACTED]	[REDACTED]
[REDACTED]	[REDACTED]	[REDACTED]

[REDACTED]	[REDACTED]	[REDACTED]
------------	------------	------------

[REDACTED]

[REDACTED]

[REDACTED]

[REDACTED]

[REDACTED]

[REDACTED]

[REDACTED]

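### The Phase II primary ORR omits treated subjects with under one cycle or no post-baseline scan, which biases it upward relative to everyone dosed at the RP2D

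*SAP*

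**What the plan says.** SAP 10.1 states that "ORR is the primary efficacy endpoint in phase II (without cohort C) and secondary endpoint in phase I". It defines confirmed ORR as the proportion of subjects with a "best overall response of confirmed CR or PR in EFS with measurable disease at baseline", and SAP section 10 names the same set for the ORR analysis. SAP 8.5 defines that set as "all subjects who received at least 1 cycle of OP-1250 and have at least 1 post-baseline tumor assessment". Protocol 11.3 (Overall Response Rate) applies the same filter: "Subjects with measurable disease who receive at least 1 cycle of OP-1250 and have a post treatment tumor assessment will be included".

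Protocol 8.4 adds that Part B subjects and "subjects in the Phase II portion will be replaced if they are not evaluable for response", and explains this as having "received less than 1 cycle of therapy and/or did not have a post-baseline tumor assessment". That is the complement of the EFS. Protocol 11.4.3 and SAP 5.3 say only that such subjects may be replaced; either way they are outside the ORR denominator.

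The Full Analysis Set (FAS) in SAP 8.4 is "all subjects who received at least 1 dose of OP-1250 and have at least 1 post-baseline tumor assessment", so it drops the one-cycle rule but still needs a scan. Protocol 11.3 plans efficacy analyses on both FAS and EFS; in the readable SAP text, ORR is run on the EFS only. SAP 10.5 does not impute missing disease assessments.

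**The concern.** Membership of the primary denominator depends on what happens after dosing starts. A subject who dies early, or who withdraws without a scan, is a treatment failure for response purposes, yet counts as neither failure nor success. The subject is removed and a new one enrolled. Since someone with no post-baseline scan cannot be a recorded responder, removal can only raise the rate.

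Protocol 11.4.3 says the end-of-Phase II review will cover the full group of 50 measurable-disease subjects treated at the RP2D, and SAP 5.3 describes the ORR data in similar terms. Under the EFS and replacement rules, the 50 analysed are not everyone treated. Safety, by contrast, uses all dosed subjects (SAP 8.2). The risk:benefit review would thus take risk from all treated subjects and benefit from a filtered subset.

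**Working it through.** **Inputs from the documents**
- Cohort A: about 50 subjects (SAP section 4; Protocol 8.9).
- Phase II total: 50 + 15 + 15 = 80 evaluable, with up to 88 enrolled to allow replacement (SAP section 4; Protocol 8.9). The allowance is 88 − 80 = 8. The protocol synopsis and Protocol 8.1 and 8.6 call the 88 evaluable, but the cohort sizes add to 80.
- Interval: exact two-sided 95% Clopper-Pearson (SAP 10.2).
- Stated precision: ±15% for 50 subjects and ±19% for 30 (SAP 5.2 and 5.3).
- First scheduled scan: Cycle 3, about week 8 (Protocol 10.3.1). Table 1 also places tumor assessment at the EOT visit.

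**Reproducing the plan's own figures.** The widest Clopper-Pearson interval is at 50%. For 25/50 it is 35.5% to 64.5%, a half-width of 14.5 points, which rounds to ±15%. For 15/30 it is 31.3% to 68.7%, a half-width of 18.7, which rounds to ±19%. Both stated figures hold.

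**Size of the shift.** Let r be the number of responders among 50 analysed and k the number of treated but excluded subjects with measurable disease, all counted as non-responders.
- Reported ORR = r/50
- All-treated ORR = r/(50 + k)
- Relative overstatement = (50 + k)/50 − 1 = k/50

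The documents do not give k. Three values are assumed: k = 2 (a small loss); k = 5 (Cohort A's pro rata share, 50 × 88/80 = 55 treated); and k = 8 (the whole allowance in Cohort A, the extreme within it). The relative overstatements are 2/50 = 4%, 5/50 = 10% and 8/50 = 16%. The responder counts below are also illustrative.

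| Responders | r/50 | k = 2 (r/52) | k = 5 (r/55) | k = 8 (r/58) |
|---|---|---|---|---|
| 5 | 10.0% | 9.6% | 9.1% | 8.6% |
| 10 | 20.0% | 19.2% | 18.2% | 17.2% |
| 15 | 30.0% | 28.8% | 27.3% | 25.9% |
| 20 | 40.0% | 38.5% | 36.4% | 34.5% |

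At 15 responders the exact 95% intervals are 17.9–44.6 (n = 50), 17.1–43.1 (n = 52), 16.1–41.0 (n = 55) and 15.3–39.0 (n = 58). The absolute shift is 1.2, 2.7 or 4.1 points.

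**Direction.** The one exception would be a subject with less than one cycle whose early unscheduled scan showed a response. SAP 10.1 also requires confirmation at least 28 days later, so this is remote.

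**The case against.** *Early stoppers are not all lost.* A reader might infer that the analysed subjects are simply those who survived the first 8 weeks, because the first scheduled scan is at Cycle 3. The documents do not support that. Table 1 appears to place radiology and tumor measurement at the EOT visit, and its footnote 18 applies them to subjects who have not already progressed radiologically. Protocol 10.3.2 agrees, with a waiver if an assessment was done in the previous 4 weeks. Protocol 8.3.3 and 10.5.3 ask for EOT evaluations after withdrawal where possible. A subject who completes Cycle 1, stops in week 5 or 6 and has the EOT scan is in the EFS as a non-responder. Progression seen on a scan before one cycle is completed does remove the subject from the EFS, but not from the FAS that Protocol 11.3 plans. This part of the objection stands and narrows the loss to subjects with under one cycle or no scan at all.

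*The size is small and assumed.* The 88 is a ceiling, not an expected count, and even 4.1 points lies well inside ±15. That is fair. But sampling error has no direction and this shift does; the reported interval does not reflect it.

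*The set is prespecified, and nothing is tested.* Both documents use the evaluable set consistently, there is no null rate or success rule, and SAP 9.1 already tabulates the number in each analysis set and the reasons for discontinuation. This lowers the severity. It does not remove the bias, because estimation is the stated purpose of Phase II and the disposition table is not described as split by measurable disease.

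**Conclusion.** The point holds. As written, the Phase II primary ORR is biased upward relative to all subjects with measurable disease and no CNS metastases who were dosed at the RP2D.

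The size depends on k. The range of 4% to 16% relative, or 1.2 to 4.1 points at an illustrative 30%, rests on assumed exclusions of 2 to 8 and exactly 50 analysed. It should not be read as the true error of a result not yet seen. Part B subjects at the RP2D count towards Cohort A and are replaced under the same rule, and SAP 6.1 pools subjects by dose across study parts. The actual denominator may therefore differ from 50, and exclusions are not confined to the Phase II allowance of 8.

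A reader might also infer that no all-treated analysis is planned anywhere. That can be said only of the readable text: passages beside the ORR population statements in Protocol 11.3 and SAP section 10 are redacted, and a sensitivity analysis there cannot be ruled out. The visible primary definition is still the restricted one.

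Severity is should-fix. No type I error, power or decision threshold is affected.

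**What to change.** In SAP 8.5 and section 10, define the primary ORR denominator as all subjects who received at least one dose at the RP2D and had measurable disease and no CNS metastases at baseline, including those later replaced. State that a subject without a post-baseline assessment counts as a non-responder. Keep the EFS result as supportive, and report how many treated subjects fall outside the EFS, with reasons. Align the wording of Protocol 11.3.

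At minimum, report the all-treated ORR with its exact interval beside the EFS result.

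The cost is SAP wording, the matching protocol text and one more table on data already collected. No additional subjects or procedures are needed, and the larger denominator does not worsen the stated precision. The only downside is a slightly lower reported ORR.

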8.6 Clinical Benefit Rate (CBR) Analysis Set

The CBR analysis set (CBRAS) will include subjects in EFS, who started their first dose 24 weeks before data cut off. Subjects who are on treatment for less than 24 weeks, without radiographic progression per RECIST 1.1 will be excluded.

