### 8.11 Treatment Duration

In the absence of unacceptable OP-1250 treatment-related toxicity or disease progression, subjects may receive OP-1250 treatment for up to 1 year and beyond 1 year with the agreement of the investigator or designee and the sponsor.

Treatment will continue until any 1 of the following occurs:

- SAE or AE that requires dose discontinuation as described in [Section 8.10, Table 8](#).
- Progressive disease as determined by RECIST 1.1 (see [Appendix E](#)) (Tumor marker elevations in the absence of unequivocal radiologic progression of target or non-target lesions is not considered disease progression. Per RECIST 1.1, disease progression requires an overall disease burden increase based on the change in non-measurable disease that is comparable in magnitude to the increase that would be required to declare PD for measurable disease: ie, an increase in tumor burden representing an additional 73% increase in 'volume,' which is equivalent to a 20% increase in diameter in a measurable lesion.)
- Initiation of non-protocol anticancer therapy.
- Illness or condition that may interfere with the subject's participation or require treatment discontinuation.
- Treating investigator or designee's determination that continuation of protocol therapy is not in the subject's best interests.
- Pregnancy.
- Noncompliance.
- Voluntary withdrawal of consent.
- Sponsor termination of the study.

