3. STUDY ENDPOINTS

The study endpoints of each of the 2 phases of the study are:

Phase I (Dose Escalation and Expansion)

Primary Endpoints:

- Incidence and nature of DLTs as defined in the protocol.
- MTD and/or RP2D of OP-1250 when used as a single agent.
- Incidence, nature, and severity of treatment-emergent Adverse Events (TEAEs) and serious adverse events (SAEs) according to NCI-CTCAE version 5.0.
- Plasma levels of OP-1250 at pre-defined intervals to establish PK parameters (includes maximum concentration (C_{max}), minimum concentration (C_{min}), time to maximum concentration (T_{max}), area under the curve (AUC), half-life (t_{1/2}), and OP-1250 trough concentration at steady state).

Secondary Endpoints:

- ORR by evaluation of tumor response assessments using RECIST 1.1 in subjects with measurable disease.
- CBR as defined by percent of subjects with CR + PR + SD \geq 24 weeks, by evaluation of tumor response assessments using RECIST 1.1.

• [REDACTED]

[REDACTED]

- [REDACTED]
- [REDACTED]
- [REDACTED]
- [REDACTED]
- [REDACTED]
- [REDACTED]

Phase II

Primary Endpoints:

- ORR by evaluation of tumor response assessments using RECIST 1.1 in subjects without evidence of CNS metastases who have measurable disease.
- Incidence, nature, and severity of TEAEs and SAEs according to National Cancer Institute-Common Terminology Criteria for Adverse Events (NCI-CTCAE) version 5.0.
- Plasma levels of OP-1250 at pre-defined intervals to establish PK parameters (includes C_{max}, C_{min}, T_{max}, AUC, t_{1/2}, and OP-1250 trough concentration at steady state). The results of those analyses will be reported separately in PK report.

Secondary Endpoints:

- CBR as defined by percent of subjects with a CR + PR + SD for ≥ 24 weeks, by evaluation of tumor response assessments using RECIST 1.1 in subjects without evidence of CNS metastases.

█

████████████████████

█

█

█

█

█

█

█

█

█

█

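### SAP 8.6 removes early stoppers without radiographic progression from the CBR denominator, which can only raise CBR against the SAP's own numerator

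*SAP*

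**What the plan says.** The CBR analysis set (CBRAS) is built in two steps in SAP 8.6. The entry rule is "The CBR analysis set (CBRAS) will include subjects in EFS, who started their first dose 24 weeks before data cut off". The exclusion rule is "Subjects who are on treatment for less than 24 weeks, without radiographic progression per RECIST 1.1 will be excluded". SAP 10.1 makes this the set for the result: "CBR will be summarized based on CBR Analysis Set (without cohort C) defined in 8.6".

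The numerator in SAP 10.1 reads "CBR is defined as the proportion of subjects with a confirmed CR, PR, or SD and who had been on treatment for" at least 24 weeks. Time on treatment runs from first dose "to end of treatment date for subjects discontinued treatment or to data cutoff date for ongoing subjects". The only visible rule that classes a subject as a failure is "Subjects who had disease progression per RECIST 1.1 7 days before Cycle 7 day 1 will not be considered as clinical benefit". SAP 10.5 rules out imputation of missing disease assessments, and SAP 10.2 plans an exact Clopper-Pearson interval.

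SAP section 3 words the endpoint differently: "CBR as defined by percent of subjects with a CR + PR + SD for ≥ 24 weeks". Protocol section 7 (Table 5) and section 11.3 define it in the same way. The protocol has no CBR analysis set; section 11.3 runs efficacy on the FAS and the EFS.

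Protocol 8.11 lists reasons for ending treatment that need no RECIST progression. One is "SAE or AE that requires dose discontinuation"; others are intercurrent illness, the investigator's judgement, new anticancer therapy, noncompliance and consent withdrawal.

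**The concern.** A subject who starts early enough, has a post-baseline scan and then stops at, say, week 16 for toxicity did not reach 24 weeks on treatment. Under SAP 10.1 that subject cannot be a benefit. Under SAP 8.6 the subject is not a failure either, but leaves the calculation. Membership of the denominator therefore depends on the outcome, and the more subjects stop early without a progression scan, the more non-benefit outcomes are removed.

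CBR is a secondary endpoint in both phases. The protocol (11.4.3) and SAP (5.3) name clinical benefit among the anti-tumor activity measures used to judge risk and benefit for later trials. An upward bias would carry into that planning, with an interval that gives no sign of it.

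**Working it through.** **1. Who can the exclusion sentence remove?** Take a subject who meets the entry rule, read as first dose at least 24 weeks before cut-off.

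| Status at cut-off | Time on treatment (SAP 10.1) | In CBRAS? | Can count as benefit under SAP 10.1? |
|---|---|---|---|
| Ongoing | To cut-off, so at least 24 weeks | Yes | Yes |
| Stopped at or after 24 weeks | At least 24 weeks | Yes | Yes |
| Stopped earlier, radiographic progression | Under 24 weeks | Yes | No |
| Stopped earlier, no radiographic progression | Under 24 weeks | **No** | No |

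Only the last row is removed, and nobody in it can be in the numerator.

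**2. Direction.** Let N be the EFS subjects meeting the entry rule, x those with benefit under SAP 10.1, and k those removed. With the k kept as no benefit the rate is x/N; the SAP reports x/(N-k). The ratio is N/(N-k), which exceeds 1 whenever k > 0: 50/45 = 1.11 if 10% are removed and 50/40 = 1.25 if 20% are.

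**3. The plan's own precision figure.** No planned CBR is stated, so there is none to reproduce. SAP 5.3 gives ±15% for 50 subjects. The exact 95% interval for 25/50 is 35.5% to 64.5%, a half-width of 14.5 points, which agrees. For 30 subjects (SAP 5.2, ±19%), 15/30 gives 31.3% to 68.7%, a half-width of 18.7 points, which also agrees.

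**4. Illustrative size.** Neither the early-stop share nor an expected CBR is in the documents. Assume N = 50 and x = 20.

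| k removed | Reported CBR | Exact 95% CI | Shift (points) |
|---|---|---|---|
| 0 | 20/50 = 40.0% | 26.4 to 54.8 | 0 |
| 2 | 20/48 = 41.7% | 27.6 to 56.8 | 1.7 |
| 5 | 20/45 = 44.4% | 29.6 to 60.0 | 4.4 |
| 8 | 20/42 = 47.6% | 32.0 to 63.6 | 7.6 |
| 10 | 20/40 = 50.0% | 33.8 to 66.2 | 10.0 |

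With k = 5, an assumed CBR of 30% (15/50) becomes 15/45 = 33.3%, and one of 50% (25/50) becomes 25/45 = 55.6%. For Cohorts A and B together (50 + 15 = 65), 26/65 = 40.0% becomes 26/59 = 44.1% with 6 removed and 26/52 = 50.0% with 13 removed.

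**5. Against the protocol definition.** The protocol and SAP section 3 state no time-on-treatment condition for CR or PR. If r of the k removed were confirmed responders, the rate under that definition is (x + r)/N. With N = 50, x = 20 and k = 5, CBRAS gives 44.4%, against 40%, 42%, 44%, 46%, 48% or 50% for r = 0 to 5. CBRAS is too high when r < xk/(N-k) = 100/45 = 2.2, that is for r of 2 or fewer, and too low for r of 3 or more.

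**The case against.** The strongest points on the other side are these.

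- **The bias need not be upward in every sense.** This stands. Step 5 shows that against the protocol definition the direction depends on how many of those removed had responded. A reader might infer that everyone removed lacked disease control; the documents support this only for the SAP 10.1 numerator.
- **Not every early failure is lost.** This stands. The schedule of events asks for tumor assessment at end of treatment in subjects without earlier radiologic progression, and protocol 10.5.3 asks for that visit, where possible, in withdrawn subjects. A clinical deterioration confirmed on that scan stays in as no benefit. Subjects with less than one cycle or no post-baseline scan are removed by the EFS, which the protocol itself defines, and not by SAP 8.6.
- **The effect may be small.** It may. Protocol 8.8.4 reports no AE discontinuations among 37 Phase 1b patients, but gives no length of follow-up and does not cover other reasons for stopping. It neither shows a small effect nor supports a 10% to 20% share. The actual denominator will also differ from 50, because SAP 6.1 pools 60 mg and 120 mg subjects across study parts.
- **CBR is descriptive.** It has no threshold or multiplicity control, and a reader who calls it a key endpoint goes beyond the documents. SAP 9.1 reports the size of each set and the reasons for stopping, so the loss can be traced. The reported rate and interval remain wrong all the same.
- **Redacted text may hold a supportive analysis.** It may, but the visible text makes CBRAS the set for CBR.
- **The sentence may have been meant for ongoing subjects.** The entry rule already covers them, so the sentence is then redundant and still removes others.

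**Conclusion.** The concern holds for the SAP's own CBR. Given the entry rule and the SAP 10.1 numerator, the exclusion sentence removes only subjects who cannot count as benefit, so the reported CBR is too high by N/(N-k) whenever any are removed. The direction is certain under that numerator, with the entry rule read as at least 24 weeks. The size is not known. It runs from 1.7 points with 2 of 50 removed to 10.0 points with 10 of 50 removed at an assumed CBR of 40%; the upper end is two-thirds of the stated ±15 points.

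Two stronger readings are not supported: that CBR is inflated by a known amount, and that it is necessarily inflated relative to the protocol definition. The second cannot be settled until the two definitions are reconciled. The error lies in the denominator of a secondary endpoint and should be corrected before database lock.

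**What to change.** 1. Delete the second sentence of SAP 8.6.
2. Define the CBR denominator as all EFS subjects, without Cohort C, whose first dose was at least 24 weeks before cut-off. Set the cut-off so that the Cycle 7 Day 1 scan and its visit window (±5 days) have passed, so that an ongoing subject is not failed for a pending scan.
3. State that a subject who stops early without documented clinical benefit counts as no clinical benefit, whatever the reason for stopping.
4. Reconcile the SAP 10.1 numerator with the definition in SAP section 3 and the protocol, so that a confirmed responder who stops before 24 weeks is classified the same way in each.
5. If wanted, keep the present CBRAS as a labelled sensitivity analysis.

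This keeps the protocol's EFS. Widening the denominator to all treated subjects would depart from the protocol's efficacy sets, and restricting it to subjects without CNS metastases would go beyond the SAP's removal of Cohort C; neither is needed here. Steps 1 to 3 need SAP wording only. Step 4 does too if the SAP numerator is brought into line with the protocol; the reverse would need a protocol change. No new data are collected. The cost is a somewhat less favourable reported CBR.
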